11.2.4. Stopping rules

This study does not involve major risk for participating. Nevertheless, we will follow the 2009 Recommendations of the American College of Obstetrician and Gynecologist, Committee on Obstetric Practice^[47] to determine if temporary and permanent discontinuation of the intervention of a participant is required due to the safety concerns. Modifications to the intervention or complete but temporary discontinuation will be determined on a case-by-case basis.

- Criteria for **Temporary Discontinuation** of the Intervention
 - o Severe anemia
 - Intrauterine growth restriction in current pregnancy
 - o Other complications identified by the Medical Monitor or the participant's provider
- Criteria for Permanent Discontinuation of the Intervention
 - Premature labor in current pregnancy
 - Ruptured membranes
 - o Preeclampsia
 - o Persistent second or third trimester bleeding
 - o Other complications identified by the Medical Monitor or the participant's provider

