Information will be abstracted from the LEERS records on adverse perinatal outcomes, including on the diagnosis of gestational diabetes, gestational hypertension/preeclampsia, and medically indicated Cesarean section (maternal outcomes) as well as neonatal intensive care unit admission and birth weight that will allow for calculation of small for gestational age or large for gestational age (neonatal outcomes). Specifically, we will define medically indicated Cesarean section as deliveries via Cesarean method of delivery with attempt of labor or if prior to 39 weeks with any medical indication. Small for gestational age (SGA, <10th percentile) and large for gestational age (LGA, >90th percentile) will be defined using birth weight for gestations greater than 19 weeks and less than 45 weeks based on the Alexander criteria specific for neonatal sex and rate. Preterm birth will be defined as any birth occurring prior to 37 weeks gestation; the calculation of gestational age at delivery will be determined as the difference in days between delivery date and the estimated date of conception divided by 7, with the delivery date abstracted from the birth certificate record and the date of conception calculated as 280 days prior to the participant self-reported due date.

From these outcomes, a maternal and neonatal composite will be calculated. Specifically, for each participant, the number of adverse maternal outcomes (as listed above) will be summed; from this, a binary maternal composite will be derived with any participant who has a non-zero sum indicated as having a maternal adverse outcome and those with a zero-sum having no maternal adverse outcome. A neonatal composite will be derived analogously based on the adverse neonatal outcomes (as listed above). Other study measures (e.g., baseline characteristics) are briefly defined below.

Gestational age at randomization in weeks is defined as the number of days since the date of conception divided by 7, with the date of conception calculated as 280 days prior to the participant self-reported due date.

Parity is defined categorically as either nulliparous or non-nulliparous based on participant self-report.

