4.3 Analyses of Study Aims

Hypothesis 1: The incidence of appropriate study observed GWG per week according to the 2009 Institute of Medicine guidelines¹ will be higher in the SmartMoms® group as compared to the Usual Care group.

The categorical outcome of study-observed GWG per week attainment will be analyzed using a general linear model with a fixed effect for group (SmartMoms®, Usual Care) with a binary distribution and a log odd link function modeling the incidence rates. Covariates will include BMI category (normal weight, overweight, obesity) at randomization, parity (nulliparous, non-nulliparous), and gestational age at randomization. Results will be reported as adjusted odds ratios (OR) and/or relative risks (RR) as appropriate. The analysis will also be conducted and reported within each BMI category.

Hypothesis 2: Study observed GWG seen in the SmartMoms® group will be less as compared to the Usual Care group. This will be assessed using the following three measures: study observed GWG, weekly GWG, and deviation from the 2009 Institute of Medicine guidelines.¹

The continuous outcome of study observed GWG will be analyzed using a linear mixed-effects model including fixed effects for time (early pregnancy, late pregnancy), group, and the interaction thereof, with participant as a random effect to account for within-participant repeated measures as well as BMI category (normal weight, overweight, obesity) at randomization, parity (nulliparous, non-nulliparous), and gestational age at randomization as covariates. The continuous outcomes related to study observed GWG per week assessed only during late pregnancy (i.e., weekly GWG and deviation from the 2009 Institute of Medicine guidelines) will be analyzed analogously using a linear model with a fixed effect for group and the same covariates. The analysis will also be conducted and reported within each BMI category.

Exploratory: The incidence of adverse perinatal outcomes will be less in the SmartMoms® group as compared to the Usual Care group.

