These outcomes will be analyzed analogously to the categorical outcome of study observed GWG per week attainment using a general linear model with a fixed effect for group (SmartMoms®, Usual Care) with a binary distribution and a log odd link function modeling the incidence rates, as well as BMI category (normal weight, overweight, obesity) at randomization, parity (nulliparous, non-nulliparous), and gestational age at randomization as covariates.

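### The exploratory neonatal composite pools SGA and LGA, opposite tails of birth weight, so a downward shift can partly or fully offset within it

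*SAP*

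**What the plan says.** SAP 4.2 takes from the birth records "neonatal intensive care unit admission and birth weight that will allow for calculation of small for gestational age or large for gestational age (neonatal outcomes"). It then sets the cut-offs: "Small for gestational age (SGA, <10th percentile) and large for gestational age (LGA, >90th percentile) will be defined using birth weight".

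The composite rule is given first for the mother: "a binary maternal composite will be derived with any participant who has a non-zero sum indicated as having a maternal adverse outcome". The infant's version follows: "A neonatal composite will be derived analogously based on the adverse neonatal outcomes (as listed above"). So an infant counts as an event with any of NICU admission, SGA or LGA, and all three carry the same sign and weight. Preterm birth is defined in the same paragraph, after the list of neonatal outcomes. Whether it enters the composite is not clear.

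SAP 4.3 states the exploratory hypothesis in one direction: "The incidence of adverse perinatal outcomes will be less in the SmartMoms® group as compared to the Usual Care group". Hypothesis 2 in the same section gives the expected effect on weight gain: "Study observed GWG seen in the SmartMoms® group will be less as compared to the Usual Care group". On the method, SAP 4.3 says: "These outcomes will be analyzed analogously to the categorical outcome of study observed GWG per week attainment", that is, a logistic model adjusted for BMI category, parity and gestational age at randomization. SAP 1.5 classes birth outcomes as exploratory.

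**The concern.** SGA and LGA cannot both occur in one infant. They sit at opposite ends of a single birth-weight distribution. A program that lowers weight gain could move the centre of that distribution down. LGA would then fall, as hoped, and SGA would rise. Restricted fetal growth is a matter that the protocol itself attends to: section 11.2.4 lists "Intrauterine growth restriction in current pregnancy" among its discontinuation criteria.

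A composite that scores both tails as the same event adds a fall to a rise. Its odds ratio can sit near 1, or below it, while SGA goes up. A hypothesis of fewer adverse outcomes is hard to interpret against such a measure. A line reporting no neonatal difference could be taken as reassurance on fetal growth, and a real reduction in LGA could be lost in the same figure. SAP 1.1 looks ahead to national delivery through WIC, so that line may be read widely.

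**Working it through.** **No figure to reproduce.** Neither document gives a rate, an expected effect or a power for SGA, LGA, NICU admission or the neonatal composite. What follows is an illustration under stated assumptions.

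**Inputs from the SAP.** At least 330 enrolled, 1:1, 15% attrition (2.2, 2.3): 330 × 0.85 / 2 = 140.25 per arm. Alpha is 0.05 (section 3), taken as two-sided.

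**Assumptions.** Birth weight for gestational age is normal on the z-scale and the intervention shifts it by -d SD. Control SGA and LGA rates are varied.

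**Formulas.** With Φ the normal distribution function:
- SGA on SmartMoms = Φ(Φ⁻¹(control SGA) + d)
- LGA on SmartMoms = 1 - Φ(Φ⁻¹(1 - control LGA) + d)
- SGA-or-LGA = their sum, because they are mutually exclusive

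Example, 10% and 10%, d = 0.2: SGA = Φ(-1.282 + 0.2) = 14.0%; LGA = 1 - Φ(1.282 + 0.2) = 6.9%; sum = 20.9%.

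**Results at d = 0.2, NICU left out:**

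| Control SGA / LGA | SGA after | LGA after | Sum before → after | OR, SGA | OR, sum |
|---|---|---|---|---|---|
| 10% / 10% | 14.0% | 6.9% | 20.0% → 20.9% | 1.46 | 1.06 |
| 8% / 12% | 11.4% | 8.5% | 20.0% → 19.9% | 1.48 | 0.99 |
| 7% / 15% | 10.1% | 10.8% | 22.0% → 20.9% | 1.49 | 0.94 |
| 15% / 5% | 20.1% | 3.3% | 20.0% → 23.4% | 1.43 | 1.22 |

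For small shifts, the direction of the sum depends on which tail is commoner. With equal tails the offset is nearly complete. With LGA commoner the sum can fall. With SGA commoner the offset is partial and the sum rises. Larger shifts also weaken the offset: at 10% and 10% with d = 0.3, SGA is 16.3% and the sum 22.0% (OR 1.75 against 1.13).

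**Adding NICU admission.** Assume an independent 10% rate, unchanged by treatment: composite = 1 - (1 - SGA - LGA)(0.9). At d = 0.2 the 10%/10% case goes from 28.0% to 28.8% (OR 1.04), so an unaffected third component dilutes the contrast further. If NICU admission itself rose with the harm, the composite would pick up some of it.

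**Power, 10%/10%, d = 0.2, 140.25 per arm.** Two-proportion normal approximation, pooled variance under the null, both rejection regions counted:
- SGA (10.0% to 14.0%): about 18%
- LGA (10.0% to 6.9%): about 15%
- Sum (20.0% to 20.9%): about 5%, essentially the test's alpha

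Birth records may be available for more women than late clinic weights. With all 165 per arm, power for SGA is still only about 20%.

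**The case against.** The strongest reply is that the plan most likely already gives the separate results. SAP 4.2 defines SGA, LGA and NICU admission one by one before deriving the composite. SAP 4.3 applies the logistic model to these outcomes in the plural, and SAP section 3 reports exploratory results as point estimates with 95% confidence intervals. No passage ranks the composite above its components. This stands as the natural reading, although the SAP never says outright that the components will be shown beside the composite.

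Second, a reader might infer that the composite is flat by construction and must hide harm. The documents do not support that. The 15%/5% case shows the sum rising with SGA, and the control rates are unknown. A pure downward shift is itself an assumption. The primary target in SAP 4.2 Table 4 is a two-sided range, and if the program pulled both extremes of birth weight inward, both tails would fall. For example, shrinking the SD to 0.9 of its value from 10%/10% gives 2 × Φ(-1.282/0.9) = 15.4% against 20.0%, and an either-tail measure would then serve well. Against this, Hypothesis 2 does predict lower gain on average, so a shift is a scenario the composite should be able to show.

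Third, the outcomes are exploratory and section 3 promises cautious interpretation. That limits the weight of the point. But that caution concerns multiplicity and definitive claims. It does not warn that a neutral composite may contain opposing effects.

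Fourth, SGA alone is poorly powered. True: separating the tails does not make an effect reliably detectable. It gives each tail its own estimate, whose direction can be interpreted.

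**Conclusion.** The point holds in limited form. The neonatal composite pools two opposite tails, so under a downward birth-weight shift it can stay neutral or improve while SGA rises. In the illustrations at -0.2 SD the SGA odds ratio is 1.43 to 1.49, while the odds ratio for SGA-or-LGA runs from 0.94 to 1.22 depending on the assumed control rates. The offset is near complete, or more than complete, when LGA is at least as common as SGA. It is partial when SGA is clearly commoner.

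This rests on assumed rates, an assumed shift and a normal model. The documents do not quantify a link from weight gain to birth weight and show no harm. Growth restriction appears in the protocol as a criterion for temporarily discontinuing a participant's intervention, and that is not a statement that the program causes it. Nor do the documents support saying that the trial report as a whole would conceal a rise in SGA, because separate models are probably planned. No confirmatory claim depends on the composite. It is a cheap improvement to an exploratory summary and does not threaten the primary result.

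**What to change.** In SAP 4.2, do not combine SGA and LGA in one composite. Use components that point the same way, for example NICU admission or SGA, and report LGA on its own. State in SAP 4.3 that SGA, LGA and NICU admission are each reported by arm with an estimate and 95% confidence interval.

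If the pooled composite is kept, show it only beside those separate estimates, and state that a neutral or lower pooled result is not evidence of no fetal-growth effect. In the same edit, say whether preterm birth belongs to the neonatal composite.

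The cost is some SAP wording and one recoded variable, from birth records already to be requested. The downsides are one more exploratory estimate and fewer composite events. Under the 10% illustrations for SGA, LGA and NICU, the control rate drops from 28.0% to 1 - 0.9 × 0.9 = 19.0%. At -0.2 SD the NICU-or-SGA composite then rises to 1 - (1 - 0.1397) × 0.9 = 22.6% (OR 1.24, against 1.04 for the pooled version). The change makes the result easier to interpret but does not solve the low power.

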4.3 Analyses of Study Aims

Hypothesis 1: The incidence of appropriate study observed GWG per week according to the 2009 Institute of Medicine guidelines¹ will be higher in the SmartMoms® group as compared to the Usual Care group.

The categorical outcome of study-observed GWG per week attainment will be analyzed using a general linear model with a fixed effect for group (SmartMoms®, Usual Care) with a binary distribution and a log odd link function modeling the incidence rates. Covariates will include BMI category (normal weight, overweight, obesity) at randomization, parity (nulliparous, non-nulliparous), and gestational age at randomization. Results will be reported as adjusted odds ratios (OR) and/or relative risks (RR) as appropriate. The analysis will also be conducted and reported within each BMI category.

Hypothesis 2: Study observed GWG seen in the SmartMoms® group will be less as compared to the Usual Care group. This will be assessed using the following three measures: study observed GWG, weekly GWG, and deviation from the 2009 Institute of Medicine guidelines.¹

The continuous outcome of study observed GWG will be analyzed using a linear mixed-effects model including fixed effects for time (early pregnancy, late pregnancy), group, and the interaction thereof, with participant as a random effect to account for within-participant repeated measures as well as BMI category (normal weight, overweight, obesity) at randomization, parity (nulliparous, non-nulliparous), and gestational age at randomization as covariates. The continuous outcomes related to study observed GWG per week assessed only during late pregnancy (i.e., weekly GWG and deviation from the 2009 Institute of Medicine guidelines) will be analyzed analogously using a linear model with a fixed effect for group and the same covariates. The analysis will also be conducted and reported within each BMI category.

Exploratory: The incidence of adverse perinatal outcomes will be less in the SmartMoms® group as compared to the Usual Care group.

These outcomes will be analyzed analogously to the categorical outcome of study observed GWG per week attainment using a general linear model with a fixed effect for group (SmartMoms®, Usual Care) with a binary distribution and a log odd link function modeling the incidence rates, as well as BMI category (normal weight, overweight, obesity) at randomization, parity (nulliparous, non-nulliparous), and gestational age at randomization as covariates.

